- Inclusion/exclusion criteria align with the samples that were engaged in our community-engaged foundational studies and numerous clinical trials in persons with MS and other wheelchair users such as spinal cord injury.
- Participants will be recruited using clinic visits at UTHealth Houston and Harris Health MS clinics and flyers in the local community. Specifically, [name] will facilitate contact with potential participants in the UTHealth Houston and Harris Health clinics.

Study Procedures

- Interested participants will contact the Study Coordinator for a telephone screening, which includes a comprehensive description of the study followed by screening for inclusion criteria. Participants deemed eligible for the study will then be sent a consent form to review and sign using through REDCap. When the Study Coordinator receives the signed consent form, participants will be mailed a pre-test/baseline assessment packet. The pre-test assessment packet will include Actigraph GT3X+ accelerometer and instructions to wear the accelerometer on the non-dominant wrist for 7 days as well as an order for blood sample collection at a Quest Diagnostics/LabCorp location that is convenient for them. Participants will complete a battery of questionnaires online using REDCap. When the Study Coordinator receives the accelerometer and notification that a blood sample has been collected, participants will be randomized into the exercise training intervention condition or attention/contact control condition using the REDCap randomization module. Following randomization, participants will be mailed their condition-specific program materials as well as instructions for downloading Zoom. All participants will receive behavioral coaching, which is founded in Social Cognitive Theory (SCT) behavior change principles. Each participant will meet one-on-one with the same behavioral coach, the PI, weekly for the first 8 weeks of the program, and biweekly for the last 8 weeks (total of 12 meetings). Meetings will be recorded for auditing and training purposes as outlined in the consent form. The research team created 12 SCT-based, condition-specific newsletters that serve as the curriculum underpinning each program. Post-test assessment of tertiary outcomes following the 16-week intervention will mirror baseline

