assessments. Participants will be asked to complete an additional evaluation questionnaire to assess satisfaction with the program and usability of intervention components. All participants will be invited to complete a post-test semi-structured interview via Zoom to provide feedback on their experiences and suggestions for refining the program. All participants will be compensated \$75 for completing each assessment, and an additional \$25 will be provided for those who complete the post-test interview.

- Informed Consent: Prior to completing any assessments we will review the Informed Consent document with each participant. The member of the research team will explain each section of this document and answer any questions. Participants will be asked to sign this document using REDCap before completing assessments and being enrolled in the study. Participants will be provided with a copy of the Informed Consent document for their records.
- Blood Draw (Assessment 1&2): Participants will be asked to complete a blood draw at a Quest Diagnostics location in their local community that will take approximately 30 minutes. Biological samples will be collected and stored at Quest Diagnostics using their standardized clinical trial protocol. The samples will be disposed of immediately following analyses. They will draw 4mL of blood using a standardized protocol. This is about 1 teaspoon of blood. The biomarkers they will collect include HbA1c, cholesterol, glucose, triglycerides, and insulin.
- Questionnaires (Assessment 1&2): Participants will be asked to complete a battery of questionnaires online using REDCap at each assessment that will take 20-30 minutes. The battery of questionnaires includes a demographic and clinical characteristics questionnaire; the Patient Determined Disease Steps scale for assessing clinical disability status; the Godin Leisure Time Exercise Questionnaire; Fatigue Severity Scale; McGill Pain Questionnaire; Hospital Anxiety and Depression Scale; Multiple Sclerosis Impact Scale 29 as a quality of life measure; and the Leisure Time Physical Activity Questionnaire for People with Disabilities. Participants may skip any questions that make them feel uncomfortable.

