accommodation period). Participants are then assigned to one of three trajectories of progression over the remaining 14-week period to reach a final goal of at least two, 30-minute aerobic workouts per week. Fifteen resistance training exercises were developed that include body weight movements and use of study-provided resistance bands or wrist weights for targeting upper body, core muscle groups, and lower body that are adaptable for manual or power wheelchair users. During the proposed program, participants will choose the resistance training exercises those that best suit their functional capabilities and goals. The resistance training prescription begins with 1 set of 10 repetitions of 5 exercises performed 2 days a week. Similar to the aerobic exercise prescription, three trajectories of progression for the resistance training will be used (i.e., sets, repetitions, and exercises) over the remaining 14 weeks to reach a final goal of at least 2 sets of 15 repetitions of 10 exercises. The participant manual includes instructions on precautions and safety for exercise that will be reviewed with all participants during the first coaching call. Coaches will check-in regularly with each participant to assess safety and report any adverse events to IRB.

- Wellness Intervention: The attention/contact wellness control condition will mirror the exercise training intervention condition, but focuses on implementing health behaviors other than physical activity (e.g., diet and emotional wellbeing) over 16 weeks. This program is an adapted version of the WellIMS program from [name] III clinical trial (NCT03490240) that [name] delivered and coached during an initial postdoctoral fellowship. The program is based on SCT principles of behavior change and integrates wellness resources from the NMSS. The research team has created 12 Newsletters split into six different topics, with each topic addressed in two newsletters. The topics include Stress Management, Emotional Regulation, Diet, Sleep, Balance and Fall Risk, and Fatigue. All coaching chats and newsletters will occur with the same frequency as in the exercise training intervention condition. Participants will be provided with a participant manual, logbook, and calendar. Participants will work with their behavioral coach on goal setting specific to wellness behaviors.

Data and Safety Monitoring

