contact the research team via telephone or e-mail in occurrence of an adverse event or any other problem. Life-threatening adverse events will be reported within 24 hours and serious, but non-life-threatening adverse events will be reported within three days.

Publication Plan

- The research team will submit a protocol manuscript prior to initiating recruitment and primary outcomes manuscript outlining results from this study. The final results from the study will be presented at a national rehabilitation conference.
- Aggregated data will be used for presentation or publication purposes related to reporting of results and subsequent grant proposals. Data will be reported such that the identity of all participants will be protected in all publications and presentations.
- A report of the overall study findings in lay terminology will be provided to all participants following the completion of data analyses.

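### Safety is part of the primary outcome, yet no adverse-event question is listed at post-test and none is described for people who stop coaching

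*Combined protocol and SAP*

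**What the plan says.** Study Design makes feasibility the primary outcome, with safety as one of its three parts, measured as the incidence of participants who report adverse events. Objectives sets the criterion below 10%. Neither section says whether the denominator is all 24 randomized participants or the 12 in the exercise arm.

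Two routes for learning of events are described:

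- **Active.** Study Procedures (Exercise Intervention) has coaches check in with each participant on a regular basis to assess safety. No question set, form or interval is given. The scheduled coach contacts run "weekly for the first 8 weeks of the program, and biweekly for the last 8 weeks (total of 12 meetings". For the control arm, Study Procedures (Wellness Intervention) states: "All coaching chats and newsletters will occur with the same frequency as in the exercise training intervention condition".
- **Self-initiated.** Quality control and assurance asks participants to phone or e-mail the team if an adverse event or other problem occurs. No end date is attached.

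Data and Safety Monitoring records events in REDCap for the primary outcome.

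The post-test is described as an assessment of the tertiary outcomes that repeats the baseline measures: blood draw, questionnaires and accelerometry. Two items are added. One is a survey: "Participants will be asked to complete an additional evaluation questionnaire to assess satisfaction with the program and usability of intervention components". The other is an optional feedback interview. None of these is described as asking about adverse events. No safety follow-up is described for people who stop coaching.

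**The concern.** A percentage of participants who report an event depends on who is asked and when. Here the asking is tied to coaching. A participant who stops coaching leaves the only active inquiry, and an injury or other event is a plausible reason to stop. The post-test would be the natural point to ask everyone once more, but its listed content covers tertiary outcomes and satisfaction.

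The resulting error runs in one direction. An event that nobody elicits and the participant does not volunteer is missing from the numerator. Statistics states an intent-to-treat analysis, so the person would ordinarily stay in the denominator as event-free. What is at stake is whether a trial with 12 people per arm is declared safe on incomplete information, and whether that finding is carried into the larger trial that the pilot is meant to inform.

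**Working it through.** **1. The plan's own figure.** Meetings: 8 weeks × 1 per week + 8 weeks ÷ 2 = 8 + 4 = 12, as stated. The contact rate falls from 8/8 = 1.0 to 4/8 = 0.5 per week.

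**2. Time after the last call.** The biweekly calls fall in weeks 9, 11, 13, 15 or in weeks 10, 12, 14, 16; the protocol does not say which. That leaves 1 or 0 program weeks after the last call, then the post-test period, with no active inquiry described.

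**3. How many can leave.** The retention target in Objectives is at least 80%. 0.8 × 24 = 19.2, so 20 must be retained and up to 4 may leave with the target met. This is a tolerance, not a forecast, and not every leaver need go unasked.

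**4. The safety threshold.** The largest k with k/n < 0.10:

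- n = 24: 2/24 = 8.3% passes; 3/24 = 12.5% fails.
- n = 12: 1/12 = 8.3% passes; 2/12 = 16.7% fails.

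**5. One missed participant.** Suppose three of 24 truly have an event and one of them leaves without reporting it. Kept in the denominator, the result is 2/24 = 8.3%, a pass. Dropped from it, the result is 2/23 = 8.7%, still a pass. For the exercise arm with two true cases and one missed, the figures are 1/12 = 8.3% or 1/11 = 9.1%, again a pass. The true results, 12.5% and 16.7%, both fail.

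**6. Illustration of size.** The documents give no event rate and no capture rate, so both are assumed. Let p be the true probability that a participant has an event and u the share of such participants whose event is never recorded. Then q = p(1 − u), and

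P(criterion met) = Σ from j = 0 to k of C(n, j) q^j (1 − q)^(n − j), with k = 2 for n = 24 and k = 1 for n = 12.

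| n | p | u = 0 | u = 0.10 | u = 0.25 | u = 0.50 |
|---|---|---|---|---|---|
| 24 | 0.10 | 56.4% | 63.2% | 73.3% | 88.4% |
| 24 | 0.15 | 28.0% | 35.3% | 48.3% | 73.3% |
| 24 | 0.20 | 11.5% | 16.7% | 28.0% | 56.4% |
| 12 | 0.10 | 65.9% | 70.5% | 77.4% | 88.2% |
| 12 | 0.15 | 44.3% | 50.4% | 60.2% | 77.4% |
| 12 | 0.20 | 27.5% | 33.6% | 44.3% | 65.9% |

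The last column is an extreme. If nobody but leavers were missed and leavers had events no more often than others, u could not exceed 4/24 = 16.7% at the retention floor. It could be higher if events cause people to leave.

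**The case against.** The best defence is that a second route exists. Participants are told to phone or e-mail about any event, with no link to coaching and no stated end, so leavers are not cut off. Nor does the text confine coach check-ins to the 12 calls. The interview invitation and the pain questionnaire are further contacts near the end, and the trial is a small descriptive pilot. All of this stands. It limits the gap to active inquiry and does not close it: a volunteered report is not the same as an answer to a question, and neither the interview nor the pain scale is described as asking about adverse events.

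A reader might also infer stronger points that the documents do not support:

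- *That the events most likely to decide safety are the least likely to be recorded.* No event timing is given. Participants are non-active at entry, so early events are just as possible. The outcome counts participants, so a late event in someone already counted changes nothing.
- *That load surges just as contact halves.* "The resistance training prescription begins with 1 set of 10 repetitions of 5 exercises performed 2 days a week", and progression runs "over the remaining 14 weeks to reach a final goal of at least 2 sets of 15 repetitions of 10 exercises". That is 1 × 10 × 5 = 50 to at least 2 × 15 × 10 = 300 repetitions per session, or 6-fold. But the rise spans the whole program, part of it under weekly calls, and no week-by-week values are given, so the increase within weeks 9–16 is unknown. It also concerns only one arm.
- *That biweekly calls leave weeks 9–16 unobserved.* Each call can still ask about the preceding two weeks.
- *That a 14-day interval conflicts with the rule that* "serious, but non-life-threatening adverse events will be reported within three days". The protocol does not say when that clock starts. If it started at occurrence, weekly calls would exceed it too.

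**Conclusion.** The point holds as a gap in active ascertainment of a primary outcome. No solicited adverse-event question is listed at post-test and none is described for people who stop coaching, so for them, and after the last call, the record depends on self-initiated reports. The bias, where it occurs, is toward safe. One missed participant is enough to change the result, whether the denominator is 24 or 12.

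This rests on two assumptions: that the coach check-ins apply to both arms, since the control condition is described as mirroring the exercise condition, and that a participant with no recorded event counts as event-free, which the intent-to-treat statement implies but does not spell out. How many events would be missed cannot be derived from the documents; the probabilities in the table show sensitivity only. The halved call frequency is context and not a defect in its own right. This is an inexpensive improvement worth making, not a flaw that invalidates the trial.

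**What to change.** Add a short, fixed adverse-event question set to the post-test REDCap battery, asking about the whole period since randomization. Send it at week 16 to every randomized participant in both arms, including those who stopped coaching or exercise. Its wording should follow a stated adverse-event definition, which the protocol does not yet contain.

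Compute the safety percentage in Objectives from these answers together with coach-recorded and self-reported events. State whether the denominator is 24 or 12, and report how many participants could not be asked, by arm.

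The cost is one REDCap form in a system already used for the questionnaires and the event log, a few minutes per participant, and some review of responses by existing staff so that anything newly learned enters the existing reporting process. The recorded adverse-event rate will probably rise, making the criterion harder to meet. The coaching schedule and exercise prescription stay as they are, and no extra prompts between biweekly calls are needed.

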- Acceptability will be operationalized as participant satisfaction and perceptions measured in post-intervention formative surveys and interviews. We hypothesize that a greater proportion of participants in the SPIN exercise training condition will report high satisfaction and positive perceptions regarding the exercise training program compared with the attention/contact wellness control condition.
- The study will further examine changes in scientific outcomes of interest (i.e., metabolic health, MS symptoms, and exercise behavior change) for determining effect size and sample size estimates in powering a larger clinical trial. We hypothesize that the SPIN exercise training intervention program will lead to greater improvements in metabolic health outcomes (i.e., HbA1c, cholesterol, glucose, and triglycerides), MS symptoms (i.e., fatigue, pain, depression, and quality of life) and exercise behavior compared to the attention/control wellness program.

Study Design

- Parallel group, randomized controlled trial

- The study is funded for a 2 year period and participants will be involved in study procedures for approximately 6 months.
- The primary outcome of interest is feasibility (i.e., recruitment, retention, and safety). The secondary outcome of interest is acceptability (i.e., participant satisfaction and perceptions).
- The tertiary outcomes of interest are scientific outcomes of initial efficacy(i.e., metabolic health, MS symptoms, and exercise behavior).
- Safety will be assessed in terms of incidence of participants reporting adverse events.

Study Population

- Eligibility criteria: (a) diagnosis of MS; (b) self-reported use of a wheelchair (i.e., manual wheelchair, power wheelchair, or scooter) ≥50% of the time; (c) age of 18 years or older; (d) relapse free for the past 30 days; and (e) being non-active defined as not engaging in regular physical activity (30 minutes accumulated per day) on more than 2 days of the week during the previous 6 months (i.e., not meeting current physical activity guidelines for MS). During telephone screening participants will complete an exercise pre-participation health screen and if participants report any symptoms or conditions contradictory of exercise then physician clearance will be required before enrollment.

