- Physical Activity Assessment (Assessment #1&2): Participants will be asked to complete a standard 7-day accelerometry protocol using Actigraph wGT3X-bt) accelerometers (<https://actigraphcorp.com/actigraph-wgt3x-bt/>). Participants will be asked to wear the accelerometer on your non-dominant wrist during waking hours for 7 days.
- Coaching Sessions: You will be asked to join a Zoom call with your MS Behavioral Specialist coach throughout the study. The calls will consist of obtaining feedback on your progress and discussing topics relevant to your progress in the assigned program. These calls will be recorded and kept on a HIPAA compliant OneDrive folder for three years for future training and random auditing purposes then destroyed.
- Formative Evaluation (Assessment #2): Participants will be asked to complete a brief survey, online regarding your perceptions and experiences in the exercise training program that will take approximately 5-10 minutes. Participants may skip any questions that make them feel uncomfortable. We will also invite participants to complete an interview online, using Zoom that will last 20-30 minutes to provide feedback on the program they completed.
- Exercise Intervention: The exercise program includes both aerobic and strength training components to be completed over 16-weeks. The aerobic exercise prescription is progressive and individualized. Each participant starts with a goal of 10 minutes aerobic training the first 2-week period (i.e.,

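### The plan is inconsistent about which program control participants rate for acceptability, the secondary outcome: the survey and hypothesis name the exercise program, other sections do not

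*Combined protocol and SAP*

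**What the plan says.** Objectives defines the outcome: "Acceptability will be operationalized as participant satisfaction and perceptions measured in post-intervention formative surveys and interviews". Study Design ranks it as secondary. Its hypothesis, also in Objectives, is comparative and directional: a greater proportion of the exercise arm "will report high satisfaction and positive perceptions regarding the exercise training program compared with the attention/contact wellness control condition".

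The Formative Evaluation (Assessment #2) bullet under Study Procedures then describes the survey: "Participants will be asked to complete a brief survey, online regarding your perceptions and experiences in the exercise training program". It does not limit the survey to one arm and mentions no wellness version.

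Other statements are neutral as to arm:
- The opening narrative of Study Procedures describes an "additional evaluation questionnaire to assess satisfaction with the program and usability of intervention components".
- The Formative Evaluation bullet goes on to say that the interview is "to provide feedback on the program they completed". The narrative offers it to both arms: "All participants will be invited to complete a post-test semi-structured interview via Zoom to provide feedback on their experiences".
- The Coaching Sessions bullet refers to the program to which the participant was assigned.

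The Wellness Intervention bullet states that the control program addresses behaviors other than physical activity. Objectives plans 12 participants per group. Statistics limits the analysis of this outcome to frequencies and percentages. The document describes the survey but does not show it: no items, named instrument or threshold for high satisfaction are given.

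**The concern.** A between-arm comparison of satisfaction needs each arm to rate something it has experienced, on items that mean the same in both. The survey sentence and the hypothesis both name the exercise program, and half of the randomized participants (12/24) are assigned to something else. A control participant given such items can only skip them, answer neutrally, or guess.

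No test is planned, so the two raw percentages are the result for this hypothesis. What each arm was asked to rate determines what those percentages mean. A survey answered under the wrong wording cannot be repaired at analysis.

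**Working it through.** The plan gives no satisfaction rate, margin, alpha or power for acceptability, so there is no figure to reproduce. The check is mainly a comparison of texts.

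**1. What is rated, place by place**

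| Place | Object rated or discussed | Fits the wellness arm? |
|---|---|---|
| Objectives, acceptability hypothesis | Exercise training program | Not if read literally |
| Formative Evaluation, survey | Exercise training program | No |
| Study Procedures narrative, questionnaire | The program and its components | Yes, if it means the assigned program |
| Formative Evaluation, interview | Program completed | Yes |
| Coaching Sessions | Assigned program | Yes |

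The survey and interview sentences stand in the same bullet and name different objects.

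**2. What follows under each reading**

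- (a) Both arms answer exercise-worded items. Controls have nothing valid to rate.
- (b) Only the exercise arm answers them. The comparison has no control survey data.
- (c) Each arm rates its own program. The comparison is meaningful, but the hypothesis and the survey sentence are misworded. It also remains unstated whether the items are common to both arms. The components do differ: exercise prescription, bands and weights in one arm, wellness topics in the other.

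The plan does not say which reading applies.

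**3. Direction under reading (a): illustration only**

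Inputs: n = 12 per arm (Objectives). Assumed, not in the documents: a true satisfaction rate p of 50% to 90%, equal in both arms; and a share q of controls who cannot endorse an exercise-worded item and are counted as not highly satisfied.

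Exercise count X ~ Binomial(12, p). Control count Y ~ Binomial(12, p(1 − q)). The quantity is the chance that the exercise arm shows the greater proportion, P(X > Y) = Σ over i > j of P(X = i)·P(Y = j).

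| p | q = 0 | q = 25% | q = 50% |
|---|---|---|---|
| 50% | 0.419 | 0.663 | 0.862 |
| 60% | 0.418 | 0.707 | 0.907 |
| 70% | 0.412 | 0.754 | 0.944 |
| 80% | 0.398 | 0.809 | 0.972 |
| 90% | 0.359 | 0.876 | 0.991 |

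With neutral items (q = 0) and equal satisfaction, exercise comes out ahead 36% to 42% of the time. This is below half because ties are possible. With q = 25% the range is 66% to 88%, and with q = 50% it is 86% to 99%. At 10 per arm, roughly the 80% retention target (0.8 × 12 = 9.6), the three ranges are 34% to 41%, 64% to 84% and 83% to 98%.

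The table shows direction, not an expected size. The documents give neither p nor q, and they do not say how a non-applicable or skipped answer is counted, although the bullet allows questions to be skipped. If such answers were dropped instead, the control percentage would rest on few or no responses.

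**The case against.** The best defense is that the intended meaning is reasonably clear. The survey itself is not shown, only described, and one of its two descriptions is neutral. The narrative in Study Procedures follows text on condition-specific materials, so the program there most naturally means the assigned one. The interview and coaching sentences agree. The survey sentence slips into second-person wording, which suggests text carried over from participant materials, though that is an inference. The hypothesis can also be read as an ellipsis: exercise participants' satisfaction with their program against controls' satisfaction with theirs. The analysis is descriptive, so no type I error or power is affected. Interviews also inform acceptability, and exercise-arm ratings remain interpretable on their own.

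Most of this stands. A reader might infer that the comparison is undefined, or won by construction because a single satisfied exercise participant (1/12, or 8.3%) beats 0/12. The documents do not support that. It requires controls to receive the exercise-worded items literally, none of them to endorse those items, and non-applicable answers to count as not satisfied. The plan states none of these.

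The conflict itself is not answered. Neutral wording in one place does not override specific wording in two others, one of which is the description of the survey and the other the hypothesis it serves. Silence on item wording does not show that the items differ between arms, but it does not secure common items either.

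**Conclusion.** The point holds as an inconsistency with a possible bias, not as a demonstrated invalid comparison. Two places name the exercise program as the thing rated, other places are neutral, and half the randomized participants do not receive the exercise program. If the survey is fielded as the Formative Evaluation bullet words it, control ratings have no valid object and the descriptive comparison would tend to favor exercise. The size of this cannot be derived from the documents, and the figures above depend on assumed values of p and q. If each arm rates its own program, the bias does not arise and only the wording is at fault. The consequence is moderate: it affects the secondary outcome's only hypothesis, but not the primary feasibility outcomes or any formal test.

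**What to change.** 1. In Objectives, reword the acceptability hypothesis so that each arm's satisfaction and perceptions concern the program that arm was assigned.
2. In the Formative Evaluation bullet, make the same change to the survey sentence, so that it agrees with the interview sentence beside it.
3. In the REDCap survey, include one block of satisfaction and perception items worded identically for both arms, and state that the between-arm comparison uses only this block.
4. Report exercise-specific usability items for the exercise arm only.

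While the form is open, it would be sensible to state the cut-off for high satisfaction and how skipped items are counted. The plan gives neither, though that is a separate gap.

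The cost is edits to two sentences and one existing form, with no added participants or assessments. The downside is small: component-specific items drop out of the between-arm comparison.
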